- The Symptom Reporting eDiary will be activated for collection of ILI and COVID-19 symptoms.
- Symptom Reporting eDiary: Participants will be instructed to report via eDiary or telephone calls whether ILI and/or COVID-19 symptoms have been experienced on the following schedule: Once weekly from Day 1 through Day 181/EoS, if symptoms occur, participants will be directed to return to the study site as soon as possible, but no later than 72 hours after the onset of symptoms, for medical evaluation and an NP swab.
- Trained study personnel will call all participants to collect information related to any SAEs, MAAEs, AESIs, AEs leading to discontinuation, information on concomitant medications associated with those events, and any non-study vaccinations.
- All concomitant medications and non-study vaccinations will be recorded through 28 days after vaccination; all concomitant medications relevant to or for the treatment of an SAE, AESI, or MAAE will be recorded from Screening through Day 181/EoS. Historical use of facial injections and dermal fillers for cosmetic or medical indications such as migraine headaches will also be collected.

TABLE OF CONTENTS

CLINIC	AL STUDY PROTOCOL	1
PROTO	COL APPROVAL – SPONSOR SIGNATORY	2
DECLA	RATION OF INVESTIGATOR	3
PROTO	COL AMENDMENT SUMMARY OF CHANGES	4
1.	PROTOCOL SUMMARY	9
1.1.	Synopsis	9
1.2.	Schema	25
1.3.	Schedule of Events	26
TABLE	OF CONTENTS.	29
LIST O	F TABLES	36
LIST O	F FIGURES	36
LIST O	F ABBREVIATIONS AND DEFINITION OF TERMS	37
2.	INTRODUCTION	40
2.1.	Background and Overview	40
2.1.1.	mRNA-1010	41
2.1.2.	mRNA-1273	41
2.1.3.	mRNA-1073	42
2.2.	Study Rationale	42
2.2.1.	Nonclinical Studies	42
2.2.2.	Clinical Studies	44
2.3.	Benefit/Risk Assessment	45

	aTX, Inc. 1073-P101 Protocol Amendment 2	mRNA-1073
2.3.1.	Potential Benefits of Study Participation	45
2.3.2.	Risks from Study Participation and Their Mitigation	45
2.3.3.	Overall Benefit/Risk Conclusion	46
3.	OBJECTIVES AND ENDPOINTS	48
4.	STUDY DESIGN	50
4.1.	General Design	50
4.2.	Scientific Rationale for Study Design	52
4.3.	Choice of Vaccine Doses	53
4.4.	End of Study Definition	54
5.	STUDY POPULATION	55
5.1.	Inclusion Criteria	55
5.2.	Exclusion Criteria	56
5.3.	Lifestyle Restrictions	57
5.4.	Screen Failures	58
6.	STUDY TREATMENT	59
6.1.	Investigational Products Administered	59
6.2.	Randomization and Blinding	59
6.3.	Preparation/Handling/Storage/Accountability	60
6.3.1.	Preparation of Study Vaccine	60
6.3.2.	Study Vaccine Administration	60

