3. OBJECTIVES AND ENDPOINTS

The objectives and endpoints of this study are described in Table 2.

Table 2 Study Objectives and Endpoints

Objectives	Endpoints
·	"F"
To evaluate the safety and reactogenicity of study vaccines	 Frequency and grade of each solicited local and systemic reactogenicity AR during a 7-day follow-up period post vaccination Frequency and severity of any unsolicited AEs during the 28-day follow-up period post vaccination Frequency of any SAEs, AESIs, MAAEs, and AEs leading to discontinuation from Day 1 to Day 181/EoS
Secondary	
To evaluate the humoral immunogenicity to vaccine-matched strains for influenza and SARS-CoV-2 across study vaccine arms at Day 29	 GMT and GMFR at Day 29 compared with Day 1 (baseline) by HAI assay for influenza and PsVNA (or binding antibody assay) for SARS-CoV-2 Influenza: Percentage of participants with seroconversion, defined as a Day 29 titer ≥ 1:40 if baseline is < 1:10 or a 4-fold or greater rise if baseline is ≥ 1:10 in anti-HA antibodies measured by HAI assay SARS-CoV-2: Percentage of participants with seroresponse, defined as a Day 29 titer ≥ 4-fold if baseline is ≥ LLOQ or ≥ 4 × LLOQ if baseline titer is < LLOQ in nAb titers measured by PsVNA (or binding antibody assay)
To evaluate the humoral immunogenicity to vaccine-matched strains for influenza and SARS-CoV-2 at all evaluable humoral immunogenicity time points	 GMT and GMFR compared with Day 1 (baseline) by HAI for influenza and PsVNA (or binding antibody assay) for SARS-CoV-2 Percentages of participants with seroconversion (influenza) and seroresponse (SARS-CoV-2) as defined above

Objectives	Endpoints
Exploratory (may be performed)	
To evaluate the humoral immunogenicity against vaccine mismatched strains	GMT and GMFR (compared to Day 1) to vaccine mismatched strains
To evaluate the humoral immunogenicity against vaccine-matched and mismatched strains using alternative methods	GMT and GMFR (compared to Day 1) to vaccine-matched and mismatched strains assayed by alternative methods (eg, microneutralization assay for influenza or ligand-binding assay for SARS-CoV-2)
To evaluate cellular immunogenicity in a subset of participants	Frequency, magnitude, and phenotype of virus-specific T-cell and B-cell responses measured by flow cytometry or other methods, and to perform targeted repertoire analysis of B cells and T cells after vaccination

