5.3. Lifestyle Restrictions

Participants must not eat or drink anything hot or cold within 10 minutes before oral temperature is taken. Participants in the study should defer vaccination with an approved COVID-19 vaccine

mRNA-1073

or seasonal influenza vaccine until after completion of their Day 29 visit, and ideally until Day 181 visit, if such vaccines are available, and they have discussed with the investigators and have chosen to receive it.

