6.5.2. Concomitant Medications and Therapies

At study site, study staff must question the participant regarding any medications taken and non-study vaccinations received by the participant and record the following information in the eCRF:

- All non-study vaccinations administered within the period starting 28 days before the study injection and through Day 181/EoS.
- Any seasonal influenza vaccine administered since April 2021.
- Any authorized or investigational COVID-19 vaccine at any time before the IP injection.
- All concomitant medications taken through 28 days after vaccination. Antipyretics and analgesics taken prophylactically (ie, taken in the absence of any symptoms in anticipation of an injection reaction) will be recorded as such.
- Systemic steroids (≥ 10 mg/day of prednisone or equivalent), immunosuppressants, immune-modifying drugs, immunoglobulins, and/or blood products administered at any time during the study period after the IP injection.
- Any concomitant medications used to prevent or treat COVID-19 or its symptoms.
- Any concomitant medications relevant to or for the treatment of an SAE, AESI, or an MAAE from Day 1 through Day 181/EoS.
- The participant will be asked in the eDiary if they have taken any antipyretic or analgesic to treat or prevent fever or pain within 7 days after vaccination, including the day of injection. Reported antipyretic or analgesic medications should be recorded in the source document by the study site staff during the post-injection study visits or via other participant interactions (eg, telephone calls).
- Historical use of facial injections or dermal fillers, for cosmetic or medical indications such as migraine headaches.

Concomitant medications (including vaccinations) will be coded using the WHO Drug Global.

If a participant takes a prohibited drug therapy, the investigator and the contract research organization's (CRO's) medical monitor will make a joint decision about continuing or withholding further injection of the participant based on the time the medication was administered, the drug's pharmacology and pharmacokinetics, and whether use of the medication will compromise the participant's safety or interpretation of the data. It is the investigator's responsibility to ensure that details regarding the concomitant medications are adequately recorded in the eCRF.

6.5.3. Concomitant Medications and Vaccines That May Lead to the Elimination of a Participant From Per-Protocol Analyses

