The use of the following concomitant medications and/or vaccines will not require withdrawal of the participant from the study but may determine a participant's evaluability in the per-protocol (PP) analysis (analysis sets are described in Section 9.4):

- Any investigational or nonregistered product (drug or vaccine) other than the IPs used during the study period.
- Immunosuppressants or other immune-modifying drugs administered chronically (ie, more than 14 days in total) during the study period. For corticosteroids, this will mean that prednisone ≥ 10 mg/day or the equivalent is not permitted. Inhaled, nasal, and topical steroids are allowed.
- Long-acting immune-modifying drugs administered at any time during the study period (eg, infliximab).
- An authorized or licensed vaccine administered during the period from 28 days before through 28 days after vaccination.
- Immunoglobulins and/or any blood products administered during the study period.
- Antiviral and antiretroviral medications.

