9.4. Analysis Sets

The analysis sets are described in Table 8.

Table 8 Analysis Sets

Set	Description	
Randomization Set	The randomization set consists of all participants who are randomly assigned.	
FAS ¹	The FAS consists of all randomly assigned participants who receive the IP.	
PP Set ²	The PP set consists of all participants in the FAS who comply with the injection schedule, comply with the timings of immunogenicity blood sampling to have a baseline and at least 1 post-injection assessment, do not have influenza or SARS-CoV-2 infection at baseline and post-baseline up to Day 29 (as documented by positive RT-PCR testing result), and have no major protocol deviations and/or prohibited concomitant medication use (documented in the Section 6.5.3) that are prespecified with impacts on the immune response and should be excluded from the PP set.	
Safety Set ³	The safety set consists of all randomly assigned participants who receive the IP.	

Set	Description	
Solicited Safety Set ⁴	The solicited safety set consists of all participants in the safety set who contribute any solicited AR data.	

Abbreviations: AR = adverse reaction; FAS = full analysis set; IP = investigational product; PP = per-protocol.

- ¹ For the FAS, participants will be analyzed according to the group to which they were randomized.
- ² The PP set will be used as the primary analysis set for analyses of immunogenicity unless otherwise specified. Participants will be analyzed according to the group to which they were randomized.
- ³ The safety set will be used for all analyses of safety, except for the solicited ARs. Participants will be included in the vaccination group corresponding to what they actually received.
- ⁴ The solicited safety set will be used for the analyses of solicited ARs and participants will be included in the vaccination group corresponding to what they actually received.

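### The per-protocol set stops screening for infection and licensed vaccination at about Day 29 but is also the primary set at Day 181, so the descriptive Day 181 persistence results absorb later exposures

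*Protocol*

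**What the plan says.** Section 9.4, Table 8, defines a single participant-level per-protocol (PP) set. One condition is that participants "do not have influenza or SARS-CoV-2 infection at baseline and post-baseline up to Day 29 (as documented by positive RT-PCR testing result"). Another refers to Section 6.5.3, which lists products that may affect evaluability. For marketed vaccines that list reads "An authorized or licensed vaccine administered during the period from 28 days before through 28 days after vaccination". Two other entries have a different time frame: "Any investigational or nonregistered product (drug or vaccine) other than the IPs used during the study period" and, with no time limit at all, "Antiviral and antiretroviral medications".

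The PP set is primary for immunogenicity unless stated otherwise. Section 9.5.3 applies it to GMT and GMFR at each post-baseline time point, to seroconversion, and to between-group GMR and rate differences. A secondary objective in Section 3 is "To evaluate the humoral immunogenicity to vaccine-matched strains for influenza and SARS-CoV-2 at all evaluable humoral immunogenicity time points". Section 4.1 schedules blood draws on Days 1, 8, 29 and 181, and Section 9.6.2 takes the final analysis through Day 181.

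Section 5.3 asks participants to defer an approved COVID-19 vaccine "or seasonal influenza vaccine until after completion of their Day 29 visit, and ideally until Day 181 visit".

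On recording, the last footnote to the Schedule of Events says "All concomitant medications and non-study vaccinations will be recorded through 28 days after vaccination", while Section 6.5.2 asks for "All non-study vaccinations administered within the period starting 28 days before the study injection and through Day 181/EoS".

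**The concern.** The exclusion rule fits a Day 29 endpoint, but the set it defines is used unchanged five months later. Someone who takes a licensed influenza vaccine or has confirmed COVID-19 between Day 29 and Day 181 stays in the set, and no passage drops the later titer. The Day 181 titer then reflects the study vaccine plus the later exposure.

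The protocol itself makes such exposure likely. Section 5.3 treats waiting until Day 181 as an ideal only. The Synopsis gives US sites, first enrollment in May 2022 and last completion in December 2022. Section 2.1 says influenza cases rise in winter. Section 4.3 notes an authorized second COVID-19 booster for people aged 50 and older, and ages 50 to 75 form one of the two randomization strata.

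At stake is what the Day 181 figures mean. They are the trial's only humoral persistence data after Day 29, and they would look better than the study vaccines alone produce.

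**Working it through.** **The plan's own figures.** The only calculation in the protocol is Table 7, the chance of seeing at least one adverse event. 1 − (1 − p)^n gives 92.3%, 78.2%, 95.2% and 86.7%, matching all four rows. It does not bear on this point.

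**Uncovered time.** Follow-up from Day 1 to Day 181 is 180 days. The infection and licensed-vaccine limits leave Day 29 to Day 181 open: 181 − 29 = 152 days, and 152/180 = 84%.

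**Calendar.** Day 181 is 180 days after Day 1. A Day 1 of 1 May 2022 gives 28 October 2022. A Day 181 of 31 December 2022 implies a Day 1 of 4 July 2022. Day 181 visits therefore fall from about late October to the end of December.

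**Inflation within an arm.** Let f be the share of PP participants with a licensed vaccine or infection after Day 29, and k the factor by which it multiplies the Day 181 titer. On the log scale the mean rises by f × log k, so GMT and GMFR are multiplied by k^f. The documents give neither input, so both are assumptions.

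| f | k = 1.5 | k = 3 |
|---|---|---|
| 20% | 1.08 | 1.25 |
| 40% | 1.18 | 1.55 |
| 60% | 1.28 | 1.93 |

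Over a wider grid (f from 5% to 40%, k from 2 to 8) the factor runs from 2^0.05 = 1.04 to 8^0.40 = 2.30.

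**Response rates.** Suppose true Day 181 seroresponse is 50% and 90% of those with a later event meet the definition. The observed rate is (1 − f) × 50% + f × 90%, which is 54%, 58% and 62% at f = 10%, 20% and 30%.

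**Ratio against an arm with no relevant antigen.** Take influenza, with Group 1 (mRNA-1273 + placebo) as the reference. Assume a 3-fold rise there, 1.5-fold in arms that received influenza antigen, and equal uptake. A true ratio of 2.0 reads 2.0 × (1.5/3)^f: 1.74, 1.52 and 1.32 at f = 20%, 40% and 60%.

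**Ratio between two antigen-containing arms.** With a common k, the distortion is k^(f1 − f2). At equal uptake this is k^0 = 1.00, so nothing changes. With event shares of 10% and 30%, a true ratio of 1 reads 0.87, 0.76 and 0.66 for k = 2, 4 and 8.

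**The case against.** The strongest reply is that handling of individual samples belongs in the SAP, which is not at hand. Table 8 applies the PP set unless otherwise specified, the secondary objective is limited to evaluable time points, and Section 9.5.3 leaves detail on between-group comparisons to the SAP. That room exists, so the SAP may already censor these titers. But the protocol does not simply stay silent. It states a cut-off, ties it to Day 29, and applies the resulting set at Day 181. Neither phrase supplies another rule. The introduction to Section 9 also says that changing the statistical methods for secondary objectives after study start calls for an amendment, although it lets changes to other secondary analyses be listed in the SAP or study report. The optional FAS analysis has no infection or vaccine exclusion, so it does not close the gap.

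Several stronger readings are tempting and are not supported:

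- *That all non-study vaccines escape after Day 29.* Investigational or nonregistered products remain excludable throughout the study. The gap concerns authorized or licensed vaccines. Antiviral use, with no time limit, may also remove some treated late infections, though not untreated ones.
- *That all group ratios shrink toward 1.* The stated design compares mRNA-1073 with co-administration and with each vaccine alone. For influenza the natural comparators, Groups 2 and 3, both received antigen. Section 9.6.1 keeps participants and site staff blinded until final database lock, so the documents give no reason for vaccine uptake to differ by arm.
- *That a late antiviral course necessarily deletes a valid Day 29 result.* Section 6.5.3 says only that such use may affect evaluability, and Table 8 limits exclusion to prespecified cases with impact on the immune response. The text leaves the possibility open without requiring it.
- *That later vaccinations go unrecorded.* The footnote does not say recording stops, and the Schedule of Events row, the safety-call footnote and Sections 4.1, 6.5.2 and 8.1.2 all collect them later. It is a wording conflict.

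The size is also fairly challenged. Every f and k is assumed. The assays target the strains of the 2022 Southern Hemisphere vaccine, and the documents do not say whether a licensed vaccine taken by US participants in autumn would match them.

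**Conclusion.** The point stands for Day 181. Following the protocol as written, Day 181 GMT, GMFR, seroconversion and seroresponse in the primary set include titers drawn after later infection or licensed vaccination, so persistence is overstated. The direction rests on the text together with the expectation that some participants will have such events and that these raise titers. The size rests wholly on assumed inputs: a factor of 1.08 to 1.28 on GMT for a 1.5-fold rise at 20% to 60% uptake, and more for larger rises. Ratios are pulled toward 1 mainly where the reference arm received no relevant antigen (Group 1 for influenza, Group 2 for SARS-CoV-2).

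A reader might infer that the interim results are compromised. They are not affected by these later events, because they use data up to Day 29. No error rate or sample size changes either, since Section 9.2 rules out formal testing and the primary objective is safety. This should be fixed because it alters what a secondary endpoint means, but it does not threaten the trial's main conclusions.

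**What to change.** In Sections 9.4 and 9.5.3:

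1. Keep the present PP definition for visits through Day 29.
2. For Day 181, and separately for each virus, exclude titers drawn after a non-study vaccine against that virus or an RT-PCR-confirmed infection with it. Keep all earlier samples from the same participant.
3. As sensitivity analysis, show Day 181 in the same PP set without this exclusion. The FAS is not a clean substitute, because it also readmits infections before Day 29 and protocol deviations.
4. State that a Section 6.5.3 medication started after Day 29 does not remove results from Day 29 or earlier, so that the Day 29 endpoint does not change between the interim and final analyses for that reason.
5. Reconcile the Schedule of Events footnote on non-study vaccinations with the corresponding row and Section 6.5.2.

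The cost is wording and one derivation. Sections 4.2 and 6.5.2 already provide for infection and vaccination data through Day 181. Three downsides should be named. There will be fewer Day 181 values. Excluding infected participants conditions on an event after randomization that vaccination may itself affect, and Groups 1 and 2 each lack one antigen. Swabs after Day 1 are driven by symptoms, so asymptomatic infections will be missed and some contamination will remain.

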9.5. Statistical Methods

9.5.1. Baseline Characteristics and Demographics

Demographic variables (eg, age, gender, race, ethnicity, height, and weight) and baseline characteristics will be summarized by descriptive statistics for participants in the FAS.

9.5.2. Safety Analyses

All safety analyses are descriptive in nature and will be based on the Safety Set, except summaries of solicited ARs, which will be based on the Solicited Safety Set. All safety analyses will be provided by study arm. Participants will be included in the vaccination group corresponding to what they actually received. Local solicited reactogenicity analysis will be presented by study group and for each injection content, respectively.

Safety and reactogenicity will be assessed by clinical review of all relevant parameters, including solicited ARs (local and systemic ARs); unsolicited AEs (including any clinical safety laboratory abnormalities); treatment-related AEs; severe AEs, SAEs, MAAEs, AESIs, and AEs leading to withdrawal from study participation; vital sign measurements; and physical examination findings.

The number and percentage of participants with any solicited local AR, with any solicited systemic AR, with any solicited AR during the 7-day follow-up period after each vaccination, and with any Grade 3 or higher solicited AR will be summarized. A 2-sided 95% exact confidence interval (CI) using the Clopper-Pearson method will be provided for the percentage of participants with any solicited AR.

The number and percentage of participants with unsolicited AEs, treatment-related AEs, severe AEs, SAEs, MAAEs, AESIs, and AEs leading to withdrawal will be summarized. Unsolicited AEs will be presented by MedDRA system organ class and preferred term. Unsolicited AEs will be coded according to the MedDRA Dictionary for AR Terminology.

The number of events of solicited ARs, unsolicited AEs/SAEs, MAAEs, AEs leading to withdrawal, and AESIs will be reported in summary tables accordingly. Pregnancy outcomes will also be summarized.

Table 9 summarizes the analysis strategy for safety parameters. For all other safety parameters, descriptive summary statistics will be provided. Further details will be described in the SAP.

 Table 9
 Analysis Strategy for Safety Parameters

Safety Endpoint	Number and Percentage of Participants, Number of Events
Any Solicited AR (overall and by local, systemic)	X
Any Unsolicited AE	X
Any SAE	X
Any Unsolicited MAAE	X
Any Unsolicited AESI	X
Any Unsolicited Treatment-Related AE	X
Any Treatment-Related SAE	X
Any Unsolicited AE Leading to Withdrawal From Study Participation	X
Any Severe Unsolicited AE	X
Any Treatment-Related Severe Unsolicited AE	X

Abbreviations: AE = adverse event; AESI = adverse event of special interest; AR = adverse reaction; CI = confidence interval; MAAE = medically attended adverse event; SAE = serious adverse event. Notes: 95% CI using the Clopper-Pearson method; X = results will be provided.

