Myalgia (muscle aches all over body)	No interference with activity	Some interference with activity	Significant; prevents daily activity	Requires emergency room visit or hospitalization
Arthralgia (joint aches in several joints)	No interference with activity	Some interference with activity	Significant; prevents daily activity	Requires emergency room visit or hospitalization

Reaction	Grade 1	Grade 2	Grade 3	Grade 4
Nausea/vomiting	No interference with activity or 1-2 episodes/ 24 hours	Some interference with activity or > 2 episodes/24 hours	Prevents daily activity, requires outpatient intravenous hydration	Requires emergency room visit or hospitalization for hypotensive shock
Chills	No interference with activity	Some interference with activity not requiring medical intervention	Prevents daily activity and requires medical intervention	Requires emergency room visit or hospitalization
Fever (oral)	38.0-38.4°C 100.4-101.1°F	38.5-38.9°C 101.2-102.0°F	39.0-40.0°C 102.1-104.0°F	> 40.0°C > 104.0°F

Abbreviations: AE = adverse event; eCRF = electronic case report form.

Note: Events listed above but starting > 7 days post study injection will be recorded on the AE page of the eCRF. Causality for each event will be determined per assessment by the Investigator.

Source: Modified from DHHS 2007.

Any solicited AR that meets any of the following criteria must be entered into the participant's source document and must also be recorded by the study site staff on the reactogenicity page of the participant's eCRF:

- Solicited local or systemic AR that results in a visit to a healthcare practitioner (HCP), to be recorded as an MAAE (Section 8.4.4).
- Solicited local or systemic AR leading to the participant withdrawing from the study or the participant being withdrawn from the study by the investigator (AE leading to withdrawal).
- Solicited local or systemic AR lasting beyond 7 days post injection.
- Solicited local or systemic AR that otherwise meets the definition of an SAE.

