8.4.4. Medically Attended Adverse Events

An MAAE is an AE that leads to an unscheduled visit to an HCP, including telephone calls. This would include visits to a study site for unscheduled assessments (eg, abnormal laboratory follow-up, COVID-19 [Section 8.1.8]) and visits to HCPs external to the study site (eg, urgent care, primary care physician). Investigators will review unsolicited AEs for the occurrence of any MAAEs. Unsolicited AEs will be captured on the AE page of the eCRF.

All cases of RT-PCR-confirmed ILI and/or confirmed COVID-19 will be recorded as MAAEs.

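### Table 9 limits the MAAE and withdrawal rows to unsolicited events, which contradicts the third primary endpoint, Section 8.4.3 and the prose of Section 9.5.2

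*Protocol*

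**What the plan says.** The third primary endpoint (Protocol Section 3, Table 2) is "Frequency of any SAEs, AESIs, MAAEs, and AEs leading to discontinuation from Day 1 to Day 181/EoS". It is not limited to unsolicited events.

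Section 8.4.3 lists the solicited reactions that site staff must also enter on the reactogenicity page of the eCRF. Two entries matter here: "Solicited local or systemic AR that results in a visit to a healthcare practitioner (HCP), to be recorded as an MAAE", and "Solicited local or systemic AR leading to the participant withdrawing from the study", which the protocol labels as an AE leading to withdrawal.

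Table 9 in Section 9.5.2 sets out the analysis strategy for safety. Its rows include "Any Unsolicited MAAE", "Any Unsolicited AESI" and "Any Unsolicited AE Leading to Withdrawal From Study Participation". The SAE row carries no such limit. Solicited reactions have their own row, split only into overall, local and systemic.

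The prose above Table 9 also promises summaries of MAAEs, AESIs and AEs leading to withdrawal, by participants and by events. There these categories carry no qualifier of their own.

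**The concern.** A headache or fever that starts on Day 2 and sends the participant to a clinic is an MAAE under Section 8.4.3, and the primary endpoint counts it. Table 9 has no place for it in the MAAE row. The same holds for a solicited reaction that makes a participant leave the study. The grading scale in Table 6 anticipates such cases: for several symptoms, Grade 4 is defined by an emergency room visit or hospitalization.

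The MAAE and withdrawal counts per arm are part of the primary safety description. Amendment 2 states that safety and immunogenicity data from the 550 participants will be used to select a dose level for the next study. A row that omits one kind of MAAE can only understate that arm's count. If the omitted events are more common in some arms than in others, the row would also understate the difference between arms.

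**Working it through.** **Step 1. Can such an event be unsolicited?** Section 8.4.1 treats a reaction on the solicited list as unsolicited only if it starts outside the 7-day period. Section 8.4.3 keeps a reaction that starts inside the period on the reactogenicity page, with an end date, even if it lasts beyond 7 days. A solicited reaction with onset in the window therefore never becomes unsolicited.

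**Step 2. The passages side by side.**

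| Place | MAAE | AE leading to withdrawal |
|---|---|---|
| Section 3, primary endpoint | any | any |
| Section 8.4.3 | includes a solicited reaction with a healthcare visit | includes a solicited reaction that causes withdrawal |
| Section 8.4.4, definition | any AE with an unscheduled visit | not addressed |
| Section 9.5.2, prose | no qualifier of its own | no qualifier of its own |
| Section 9.5.2, Table 9 | unsolicited only | unsolicited only |

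Table 9 is the only entry with the restriction. The word carries meaning there, because the SAE row of the same table omits it.

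**Step 3. Direction.** The events in the Table 9 rows are a subset of those in the endpoint, so each row is at most the endpoint count. It is lower whenever a participant's only qualifying events are solicited reactions.

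**Step 4. Size.** The protocol gives no rate for solicited reactions that lead to a visit or to withdrawal, so the undercount cannot be computed. It can only be illustrated with the formula behind Table 7, the chance of at least one event among n participants, 1 − (1 − p)^n.

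The formula reproduces Table 7:
- n = 50, p = 0.05: 1 − 0.95^50 = 92.3%
- n = 50, p = 0.03: 1 − 0.97^50 = 78.2%
- n = 100, p = 0.03: 1 − 0.97^100 = 95.2%
- n = 100, p = 0.02: 1 − 0.98^100 = 86.7%

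This confirms the formula only. It says nothing about how often the omitted events occur.

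Now let p be the assumed proportion of an arm that the row omits:

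| Assumed p | Expected omitted, n = 100 (100p) | Chance of at least one, n = 100 | Expected omitted, Group 1, n = 50 (50p) | Chance of at least one, n = 50 |
|---|---|---|---|---|
| 0.5% | 0.5 | 39.4% | 0.25 | 22.2% |
| 1% | 1 | 63.4% | 0.5 | 39.5% |
| 2% | 2 | 86.7% | 1 | 63.6% |
| 3% | 3 | 95.2% | 1.5 | 78.2% |

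Across all 550 participants, the same rates would give 2.75, 5.5, 11 and 16.5 omitted on average (550p).

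**The case against.** The strongest reply is that nothing is lost. The prose of Section 9.5.2 promises MAAE, AESI and withdrawal summaries without this limit, promises descriptive summaries for other safety parameters, and defers detail to the SAP. The events also stay visible elsewhere:

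- They count as solicited reactions, and the first primary endpoint reports those by grade. Reactions of Grade 3 or higher have a summary of their own.
- If serious, they count in the unrestricted SAE row.
- A Grade 4 solicited reaction with no other reasonable cause meets Pause Rule 2 and brings an unscheduled DSMB review.
- Section 7.3 lists a solicited reaction as a separate reason for withdrawal and requires withdrawals for AEs to be distinguished from others.

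Most of this stands, and it rules out a stronger reading. A reader might infer that these reactions disappear from the primary safety endpoint, or that severe ones go unseen. The documents do not support that. The data are collected and the events are reported in other tables. The defect is in two row definitions.

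Two further inferences also fail. One is that MAAEs are sought only among unsolicited AEs, because Section 8.4.4 says "Investigators will review unsolicited AEs for the occurrence of any MAAEs". That sentence does not exclude other sources, and Section 8.4.3 already orders the recording. The other is that the AESI row loses events to a similar extent. The solicited terms in Table 6 have almost no overlap with the AESI concepts in Appendix 3; the exception is Grade 4 necrosis or exfoliative dermatitis.

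The reply does not remove the contradiction. The prose supports the broad reading, although the word unsolicited at the head of the participant list could be read across the whole list. Either way, Table 9 is the more specific statement and it says otherwise. The clause on other safety parameters does not help, because MAAEs and withdrawals already have rows in the table. Nor does the solicited row replace them: it does not separate a headache that led to a clinic visit from a mild one. Deferral to the SAP covers detail left open, whereas here the protocol fixes a rule that conflicts with its own primary endpoint. Section 9 requires an amendment if methods for primary objectives change after the study has begun.

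**Conclusion.** Wrong as written. The MAAE and withdrawal rows of Table 9 conflict with the third primary endpoint, with Section 8.4.3 and with the prose of Section 9.5.2. If the table is followed, solicited reactions that led to a healthcare visit or to withdrawal are left out of those rows, and the counts can only be too low.

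The size is unknown. The range of 39% to 95% for at least one omitted participant in an arm of 100 rests entirely on assumed rates of 0.5% to 3%. The 2% and 3% figures appear in Table 7 as general AE rates, not as rates of medically attended reactions. A reader might also infer that the shortfall would be worst in the most reactogenic arms. That is plausible, but the protocol gives no figures by arm to show it.

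This is a moderate consistency correction. All analyses are descriptive (Section 9.2), and data collection, safety oversight and the reporting of solicited reactions by grade are unaffected. The AESI row has the same wording problem with little practical effect.

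**What to change.** In Table 9, relabel the two rows *Any MAAE* and *Any AE leading to withdrawal from study participation*. State that each covers solicited and unsolicited events, pooled from the reactogenicity and AE pages of the eCRF, with each participant counted once per row. Keep the unsolicited-only counts as sub-rows. Relabel the AESI row in the same way for consistency.

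Optionally, extend the review sentence in Section 8.4.4 to solicited reactions so that it matches Section 8.4.3. This is a wording change only.

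The cost is revised table shells and one derivation that pools the two pages. Section 8.4.3 already requires the data, so nothing new has to be collected.
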